7.3 Data Handling Convention for Missing Data

(1) Non-PK related

Adverse events:

If severity or relationship should be missing, the most severe or more related category will be imputed for the summary.

Other safety:

For safety summaries, only observed data will be used. Unless otherwise specified, missing safety data will not be imputed.

(2) PK related

For PK summaries, only observed data will be used. Missing plasma concentration data will not be imputed.

8 STATISTICAL METHODOLOGY

8.1 Study Subjects

8.1.1 Subject Disposition

Subject disposition will be summarized and listed on the randomized subjects.

Randomization details will be listed on the randomized population.

8.1.2 Analysis Populations

Analysis populations will be summarized and listed on the randomized subjects.

8.1.3 Study Drug Exposure

Exposure data will be summarized and listed on the SAF.

8.1.4 Demographic and Other Baseline Characteristics

The following demographic and other baseline characteristics will be used.

	Categorical	Descriptive
Sex	Male, Female	
Age (years)		Yes
Height (cm)		Yes
Weight (kg)		Yes
BMI (kg/m ²)		Yes
Race	Japanese	
Medical history	No, Yes	
Complication	No, Yes	
Concomitant medication*	No, Yes	
Allergic history (including drug allergies)	No, Yes	
Drinking status	No ('Never'), Yes (otherwise)	
Smoking status	No ('Never'), Yes (otherwise)	

* The surface anesthesia for nasogastric tube insertion will be excluded.

Demographic and other baseline characteristics will be summarized and listed on the SAF.

8.1.5 Medical History

Medical history, complication and allergic history will be listed on the SAF.

8.1.6 Concomitant Medications

Concomitant medication will be listed on the SAF.

8.2 Safety Assessments

All safety assessments will be performed on the SAF.

8.2.1 Adverse Events

Overall occurrence of AEs will be summarized using the following categories by treatment.

- Subjects with at least one AE
- Subjects with at least one adverse drug reaction
- Subjects with at least one SAE
- Subjects with at least one serious adverse drug reaction
- Subjects with at least one AE leading to discontinuation of study drug
- Subjects with AE leading to death

The following summaries will also be presented by treatment.

- AEs by SOC and PT
- Adverse drug reactions by SOC and PT
- AEs by SOC, PT and severity

These will be subject-based summaries - multiple occurrences of the event with the same SOC and/or PT within a subject will be counted once in the summaries by SOC and PT; multiple occurrences of the event with the same SOC and/or PT but different severity within a subject will be counted once in the maximum severity category (severe > moderate > mild).

To summarize by treatment, the AE occurred under PO/NGT treatment period will be counted as PO/NGT treatment. Period of AE occurrence is defined in 7.1.2.1 (6).

The followings will be listed.

- AE
- SAE

8.2.2 Laboratory Tests

For quantitative tests (i.e. hematology, biochemistry and coagulation), absolute values and changes from baseline will be summarized descriptively by group and visit.

For qualitative tests of urinalysis, number and percentage will be presented by group and visit. Changes from baseline to each visit will be presented as shift-table by group.

All data will be listed.

Below is a list of the laboratory test.

Laboratory Test	Parameters
Hematology	Hemoglobin, hematocrit, RBC count, WBC count, platelet count, MCH, MCHC, MCV, differential white blood count
Biochemistry	Na, K, Cl, Ca, inorganic phosphorus, urea nitrogen, creatinine, uric acid, total bilirubin, direct bilirubin, ALT, AST, γ -GTP, ALP, LDH, CK, amylase, total cholesterol, triglycerides, LDL-C, HDL-C, total protein, albumin, glucose, CRP
Coagulation test	Prothrombin time, APTT, INR*, prothrombin activity*
Urinalysis	Qualitative tests (pH, specific gravity, protein, glucose, occult blood, urobilinogen, bilirubin, ketones), sediment*

* Only for listing. Not summarized.

8.2.3 Vital Signs

Absolute values and changes from baseline will be summarized for the following parameters by treatment and time point.

- Systolic blood pressure (mmHg)
- Diastolic blood pressure (mmHg)
- Pulse rate (bpm)
- Body temperature (°C)

All data will be listed.

8.2.4 12-Lead ECGs

Absolute values and changes from baseline will be summarized for the following parameters by treatment and time point.

- Heart rate (bpm)
- PR (msec)
- RR (msec)
- QRS (msec)
- QT (msec)
- QTcF (msec)

For interpretation, number and percentage will be presented by treatment and time point. The percentage of subjects with values outside pre-defined limits will be summarized by treatment and time point.

All data (including interpretation and findings) will be listed.

8.2.5 Physical Examinations

Physical examination will be listed.

8.3 Pharmacokinetics Evaluation

Pharmacokinetic analysis will be performed on the PKPOP. Summaries of concentrations, PK parameters and statistical analysis for unchanged edaravone will be performed using data from subjects whose PK data will be available in both treatments.

8.3.1 Plasma Concentrations and Pharmacokinetic Parameters

(1) Summary tables and listings

Plasma concentrations of unchanged edaravone will be summarized by analysis time point and treatment. All plasma concentrations will also be listed.

(2) Plots of individual plasma concentrations

Individual plasma concentrations vs. actual time for unchanged edaravone will be plotted on both linear/linear and log/linear scales, both by treatment and by subject.

(3) Plots of mean plasma concentrations

Mean (+SD) plasma concentrations vs. nominal time curves will be plotted on both linear/linear and log/linear scales superimposing the treatments.

8.3.2 Pharmacokinetic Parameters

The PK parameters listed in Section 2.1.2 will be calculated for each subject using non-compartmental model. Calculations of the parameters, including supplementary parameters, are described in Appendix 1.

The PK parameters will be summarized by treatment and listed. The supplementary parameters will not be summarized but will be included in listing.

8.3.3 Analysis of Variance

AUC_{0-t} , $AUC_{0-\infty}$ and C_{max} of unchanged edaravone will be log transformed and analysed. Only subjects with the parameter value under both treatments will be analysed. Analysis of variance (ANOVA) will be used for analysis. Group, treatment, period and subject (nested in group) will be set to factors. Least squares (LS) means for each treatment will be calculated. These values will be back-transformed and shown in table. The difference of LS means between treatments (nasogastric administration minus oral administration) and 90% CI will be calculated. These values will be back-transformed, so that they show the ratio and 90% CI of PK parameters for nasogastric administration compared to oral administration.

As reference, the other pharmacokinetic parameters of unchanged edaravone will be analysed in the same way, although t_{max} will not be log transformed prior to the analysis.

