In a phase 1 study (Study MT-1186-J01) of oral edaravone in healthy adult males, 74 subjects (54 in the edaravone group and 20 in the placebo group) received single (Cohort S1 to S7) or 5-day repeated administration (Cohort M1 and M2) of edaravone oral solution or suspension at doses of 30 to 300 mg to examine PK, safety and tolerability. The effects of race and meal on PK after single administration at a dose of 200 mg were also examined.

In PK, after single administration of edaravone oral solution or suspension in the fasting state, the C_{max} was reached 0.3 to 0.4 and 0.4 to 0.8 hours after administration, respectively, followed by biphasic or triphasic excretion, with final phase $t_{1/2}$ of 2.4 to 3.2 and 5.1 to 11.8 hours, respectively. C_{max} and AUC of edaravone increased more than dose proportional manner over a dose range of 30 to 300 mg. Plasma concentrations of sulfate conjugate and glucuronide conjugate, both are edaravone metabolites, reached C_{max} 0.5 to 1.4 hours and 0.5 to 1.1 hours after dose, respectively. They were excreted from plasma, with $t_{1/2}$ of 4.9 to 7.9 hours and 2.8 to 5.9 hours, respectively. Meal-effect examination after administration of 200 mg suspension (200 mg/10 mL 0.1% polyvinyl alcohol solution) showed that when edaravone was administered 30 minutes after a meal, C_{max} and AUC of plasma edaravone decreased

to 18.2% and 39.1% of those when it was administered in the fasting state, respectively. Comparison between plasma concentrations in Caucasian subjects and those in Japanese subjects after administration of 200 mg suspension (200 mg/10 mL) showed that C_{max} and AUC of plasma edaravone in Caucasian subjects were 75% and 79% of those in Japanese subjects, respectively. Repeated administration for 5 days did not cause accumulation in plasma concentration.

In terms of safety, no serious adverse events occurred. A total of 21 adverse events were observed in 74 subjects. Among them, the adverse event assessed as causally related to the administration was headache (1 event) in the edaravone group. The event was mild in severity and rapidly resolved. One subject in the edaravone group discontinued the study owing to adverse events. In the meal-effect cohort, moderate conjunctivitis occurred after administration of Cohort S3-1 (200 mg, a single dose in the fasting state), and administration of S3-2 (30 minutes after meal) was called off. This event was considered not related to the investigational product.

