9.2.4.1 Time points and volume of blood sampling

(1) Time points of blood sampling

Period I	Day 1	Before administration of edaravone oral suspension, 0.083, 0.25, 0.5, 0.75, 1, 1.5, 2, 4, 6, 8, 10, and 12 hours after administration
	Day 2	24 and 36 hours after administration of edaravone oral suspension
	Day 3	48 hours after administration of edaravone oral suspension
Period II	Day 4	Before administration of edaravone oral suspension, 0.083, 0.25, 0.5, 0.75, 1, 1.5, 2, 4, 6, 8, 10, and 12 hours after administration
	Day 5	24 and 36 hours after administration of edaravone oral suspension
	Day 6	48 hours after administration of edaravone oral suspension

(2) Frequency of blood sampling: 32

(3) Volume of blood sampling: 4 mL, Total: 128 mL (per subject)

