6 STATISTICAL CONSIDERATIONS

6.1 Descriptive Statistics

(1) Non-PK related

Continuous data will be summarized descriptively using the number in the analysis set (N), the number of observations (n), mean, SD, median, minimum and maximum. Categorical data will be summarized using frequency counts and percentages. The denominator for the percentages will be the total number of subjects in the treatment/group and analysis population applied, unless otherwise specified.

(2) PK related

1) Plasma concentrations

Plasma concentrations will be summarized descriptively using N, n, mean, SD, CV%, median, minimum and maximum.

2) Pharmacokinetic parameters

The plasma PK parameters will be summarized descriptively using N, n, mean (i.e. arithmetic mean), SD, CV%, median, minimum, maximum, geometric mean and geometric CV%.

CV% and Geometric CV% will be calculated as follows:

$$CV\% = \frac{SD}{\text{arithmetic mean}} \times 100$$

$$\text{Geometric CV\%} = \sqrt{[\exp(\sigma^2) - 1]} \times 100$$

where σ represents the SD calculated from the natural logarithmic transformed value of parameters.

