6.2 Statistical Tests and Estimates

No statistical tests will be performed. Confidence level will be 0.90, so that two-sided 90% CIs will be calculated where applicable.

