7.1.3.2 Pharmacokinetic Parameters

For the calculation of PK parameters, actual sampling time (in hours rounded to 3 decimal places) relative to dosing should be used. If the sampling was performed before dosing, time after dosing will be set to 0. When k_{el} is missing (or cannot be determined), $t_{1/2}$, $AUC_{0-\infty}$, $AUC\%_{ex}$, CL/F , MRT , V_z/F and V_{ss}/F will not be calculated.

(1) Below the limit of quantification

Concentration below the limit of quantification (BLQ) will be set to 0.

(2) Calculation of AUC

Timepoints with missing concentration data will be ignored. Concentration value at the end time of partial AUC will be calculated by linear-linear trapezoidal rule or by extrapolation using elimination rate constant, if there is no valid data exactly at the time.

(3) Calculation of V_{ss}/F

Pharmacokinetic parameter of V_{ss}/F will be calculated as follows:

$$V_{ss}/F = MRT \times CL/F$$

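### Does analysing tmax by untransformed ANOVA, with no rank-based interval, weaken the route comparison?

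*SAP*

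**What the plan says.** SAP 8.3.3 makes AUC0-t, AUC0-∞ and Cmax the log-transformed comparison. The model is a standard crossover ANOVA: "Group, treatment, period and subject (nested in group) will be set to factors". The remaining parameters follow for reference only: "the other pharmacokinetic parameters of unchanged edaravone will be analysed in the same way", except that tmax "will not be log transformed prior to the analysis". The tmax result is thus a difference of least squares means in hours with a 90% interval. Protocol 13.4.2 leaves tmax out of the log-transformed analysis without naming another method; the SAP, which takes precedence on statistical detail (SAP Section 1), supplies one.

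SAP 6.2 adds "No statistical tests will be performed". No margin or decision rule for tmax appears in either document.

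The ANOVA is not the only tmax output. SAP 6.1 plans for every PK parameter "SD, CV%, median, minimum, maximum, geometric mean and geometric CV"%. SAP 8.3.2 lists individual parameters, and SAP 8.3.1 plots individual concentration profiles by treatment and by subject.

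**The concern.** tmax can only fall at or near a scheduled sample. Protocol 9.2.4.1 samples at "0.083, 0.25, 0.5, 0.75, 1, 1.5, 2, 4, 6, 8, 10, and 12 hours after administration", so the gaps are about 0.25 h up to 1 h and then widen to 0.5 h and 2 h. In the earlier single-dose study (Protocol Section 1) the fasting peak came at "0.3 to 0.4 and 0.4 to 0.8 hours after administration" for solution and suspension respectively. Most values should therefore sit on a few early points, while an occasional late peak would lie 1 to 3.5 h away.

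A mean difference is sensitive to such values. A reader used to rank-based intervals for tmax would ask whether the reported difference reflects most subjects or one or two of them, and whether its interval is wider than necessary. What is at stake is the precision and reading of one supportive interval.

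**Working it through.** **Inputs from the documents.** 36 randomised, 30 completers expected and 6 dropouts (SAP 3.4; 30 + 6 = 36); two sequences; the sampling grid above; two-sided 90% intervals (SAP 6.2). The documents state no figure for tmax precision, so there is none to reproduce.

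**Assumptions, not in the documents.** 15 completers per sequence; latent tmax with median 0.5 h, log SD 0.45 and within-subject correlation 0.3, moved to the nearest sampling time; recorded times scattered by ±1 min; late peaks at the stated rate and times.

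**Methods compared.** Both use half the period difference (Period II minus Period I) for each subject.
- Planned: a two-sample t interval between sequences on 15 + 15 − 2 = 28 df, which equals the ANOVA treatment interval.
- Alternative: the Hodges-Lehmann interval, from the 73rd smallest to the 73rd largest of the 15 × 15 = 225 pairwise differences (exact level 90.2% without ties).

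**Step 1: leverage of one late peak.** Moving one tmax from 0.5 to 4 h changes that subject's half difference by 3.5/2 = 1.75 h and the ANOVA estimate by 1.75/15 = 0.12 h, about 7 minutes.

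**Step 2: validity.** With no route difference, both intervals exclude zero in about 9 to 10% of trials, as a 90% interval should. The ANOVA interval is not miscalibrated.

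**Step 3: late peaks at random in both routes** (ANOVA vs Hodges-Lehmann).

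| Late peaks | Mean width, h | Excludes 0 for a 0.25 h shift |
|---|---|---|
| none | 0.20 vs 0.19 | 99 vs 99% |
| 3% at 1.5 or 2 h | 0.27 vs 0.22 | 90 vs 96% |
| 10% at 1.5 or 2 h | 0.37 vs 0.31 | 68 vs 79% |
| 3% at 2 or 4 h | 0.41 vs 0.23 | 64 vs 95% |
| 10% at 2 or 4 h | 0.71 vs 0.36 | 31 vs 76% |

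Here late peaks are pure noise, the situation that favours a rank method. Even so, under other assumed spreads the advantage can vanish: when the bulk of tmax is already wide and late peaks reach only 1.5 h, the ratio of ANOVA to Hodges-Lehmann width is 0.95 to 0.99.

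**Step 4: late peaks under NGT only, no shift in the bulk.** In a route comparison this is itself an effect of interest.

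| Late under NGT | Excludes 0, late at 2 or 4 h | Excludes 0, late at 1.5 or 2 h |
|---|---|---|
| 10% | 40 vs 22% | 35 vs 22% |
| 20% | 85 vs 53% | 73 vs 51% |
| 30% | 98 vs 82% | 93 vs 79% |

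The order is again ANOVA vs Hodges-Lehmann, from 4,000 trials per setting; repeat runs agree within about 2 percentage points.

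The true mean difference at 10% late (2 or 4 h, average 3 h) can be checked by hand. The mean early peak is 0.5 × exp(0.45²/2) = 0.55 h, so the difference is 0.10 × (3 − 0.55) = 0.245 h. ANOVA returns 0.24 h on average and Hodges-Lehmann 0.07 h. At 20% late the estimates are 0.49 and 0.22 h.

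Nor is the rank interval always narrower. Mean widths, ANOVA vs Hodges-Lehmann, are 0.36 vs 0.39 h at 20% late (1.5 or 2 h), and at 30% late 0.40 vs 0.47 h (1.5 or 2 h) and 0.79 vs 0.95 h (2 or 4 h).

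**Step 5: ties.** SAP 7.1.3.2 says "actual sampling time (in hours rounded to 3 decimal places) relative to dosing should be used", which breaks ties only where recorded times differ from nominal. If all are exactly nominal, the Hodges-Lehmann interval excludes zero in only 0.4 to 2% of trials with no shift. With no late peaks it then detects a 0.125 h shift in 30% of trials, against 67% for ANOVA.

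**The case for a change.** The strongest case for adding a rank-based interval is Step 3. If late peaks are sporadic and unrelated to route, the ANOVA interval can be nearly twice as wide (0.41 vs 0.23 h; 0.71 vs 0.36 h) and much less sensitive to a shift of one sampling gap. A separate calculation with 18 per sequence and a different assumed spread points the same way: 0.407 vs 0.219 h with 5% of dosings late. The addition would cost one sentence and a short program, would fit a plan without tests, and could stand beside the ANOVA. The planned medians and ranges carry no interval for the route difference.

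These points stand as arithmetic and as a description of the plan. They do not show a defect. The advantage requires that late peaks occur, that they come late enough, and that they are unrelated to route; the documents support none of these with a rate or an SD. When late peaks depend on route, the alternative is the less sensitive method and shrinks the difference. The worry that one or two subjects drive the mean is met by outputs already planned: minimum, median and maximum by treatment, individual listings and subject-level profiles would show them. Excluding zero is also only a yardstick for comparing methods here, since the SAP performs no test on tmax.

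**Conclusion.** The concern does not hold. The plan does analyse tmax only by untransformed ANOVA apart from descriptive statistics, but that interval is valid, serves as reference and feeds no decision. Adding a Hodges-Lehmann interval would trade one summary for another: better when late peaks are random in both routes (95 vs 64% at 3% late, 2 or 4 h), worse when they occur under NGT only (53 vs 85% at 20% late, 2 or 4 h), and conservative if recorded times mostly equal nominal ones. Which case applies cannot be settled from the documents.

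All simulated figures rest on 30 completers and on the assumed tmax distribution and late-peak rates. The conclusion does not depend on their exact size: AUC and Cmax are unaffected, no wrong result is produced, and no finding of the trial would change. A team may prefer a rank-based summary for tmax, but the plan needs no correction.

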9 DATA PRESENTATION CONVENTIONS

9.1 Number of Digits to Report

(1) Non-PK related

Statistic	Specification	Apply to
Minimum, Maximum	Same number of DPs as provided in the datasets	All original data (i.e. non-derived)
	see section 7.3	All derived data
Mean, SD, Median	One more DP than above	All
Percentages ¹	1 DP	All

¹ Percentages: use 1 place beyond the decimal point, except for the following cases:

If the percentage is equal to 0, then not shown as "(0)" but left blank

If the percentage is equal to 100, then shown as "(100)" without a decimal

(2) PK Plasma Concentration

Statistic	Specification
Individual value	With the number of DPs to which they are reported
Mean, SD, Median, Minimum, Maximum	Same number of DPs as the individual value
CV%	1 DP

(3) PK Parameters

Statistic	Specification
Individual value	C_{\max} : same number of DPs as the plasma concentration $AUC\%_{\text{ex}}$: 3DPs t_{\max} , lower/upper limit of k_{el} : 3 DPs Adjusted R^2 : 3 DPs Number of k_{el} points: integer Other parameters: number of DPs at which minimum value of the parameter comes to 3 significant digits.
Mean, SD, Median, Minimum, Maximum, Geometric mean, LS mean, Geometric LS mean, CI	Same number of DPs as the individual values
CV%, Geometric CV%	1 DP
Ratios	3 DPs

9.2 Treatments and Groups to Report

Treatment	For TFLs
Oral administration of edaravone oral suspension 105 mg	PO
Nasogastric administration of edaravone oral suspension 105 mg	NGT

Group	For TFLs
Oral administration precedent	PO - NGT
Nasogastric administration precedent	NGT - PO

9.3 Period, Visit and Time Point to Report

(1) Non-PK related

Safety:

Period for TFLs	Visit for TFLs	Time Point for TFLs	Apply to		
			Laboratory Tests	Vital Signs	12-Lead ECGs
Screening	Screening		X	X	X
Period 1	Day -1		X	X	X
	Day 1	Pre-dose		X	X
	Day 1	1 h		X	X
	Day 2	24 h		X	X
	Day 3	48 h	X	X	X
Period 2	Day 4	Pre-dose		X	X
	Day 4	1 h		X	X
	Day 5	24 h		X	X
	Day 6	48 h	X	X	X
End of study	End of study		X	X	X

Unscheduled tests and tests on discontinuation will not be included in by-visit summaries but will be shown in listings.

(2) PK-related

Analysis Visit	Analysis Time Point
Day 1	Pre-dose, 0.083, 0.25, 0.5, 0.75, 1, 1.5, 2, 4, 6, 8, 10, 12 h
Day 2	24, 36 h
Day 3	48 h
Day 4	Pre-dose, 0.083, 0.25, 0.5, 0.75, 1, 1.5, 2, 4, 6, 8, 10, 12 h
Day 5	24, 36 h
Day 6	48 h

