9 TESTS AND OBSERVATIONS

9.1 Test/Observation Schedule

Day (time window)	Informed consent	Screening	Period I				End-of-study ^{a)} Assessment
			Day -30 to -2	-1	1	2	
Time after dosing				Visit			
Screening		X					
Written informed consent	X						
Subject characteristics	X						
Eligibility assessment	X	X					
Nasal Examination	X						
Height	X						
Weight	X	X					
BMI	X	X					
Physical examination	X	X					
Vital signs	X	X					
12-lead ECG	X	X					
Laboratory tests	X	X					
Serological tests	X						
Drug/alcohol abuse screening	X						
Pregnancy test in female	X	X					
COVID-19 virus test	X						
Dosing of edaravone				X			
Adverse events ^{b)}					X		
Concomitant medications						←	→
PK Blood sampling for edaravone						X	X

a) At the time of withdrawal, perform the same tests as would be performed in the end-of-study assessment.

b) Assess serious adverse events beginning after informed consent is obtained. Survey of other adverse events will be started after administration of the investigational product is started.

Test items	Description
Demographic and other baseline characteristics (subject characteristics)	Sex*, race*, date of birth*, body height*, body weight, BMI**, medical history*, complications*, history of allergies (including drug allergies) *, alcohol consumption*, smoking status*
Interview/physical examination	Interview/physical examination and nasal examination*
Vital signs	Blood pressure (supine), pulse rate, body temperature (axillary)
12-lead ECG	HR, QTcF, PR interval, QT interval, RR interval, QRS interval, findings
Laboratory tests	Hematology Hemoglobin, hematocrit, red blood cell count, white blood cell count, platelet count, MCH, MCHC, MCV, differential white blood count (5 differentials)
	Biochemistry Na, K, Cl, Ca, inorganic phosphorus, urea nitrogen, creatinine, uric acid, total bilirubin, direct bilirubin, ALT, AST, γ -GTP, ALP, LDH, CK, amylase, total cholesterol, triglycerides, LDL-C, HDL-C, total protein, albumin, glucose, CRP
	Coagulation test Prothrombin time, activated partial thromboplastin time
	Urinalysis Sediment, qualitative tests (pH, specific gravity, protein, glucose, occult blood, urobilinogen, bilirubin, ketones), hCG***
Serological tests*	HBs antigen, serological test for syphilis, HCV antibody, HIV antigen/antibody

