9.2.5.2 Adverse events

An adverse event (AE) is any clinically untoward or unintended sign (including an abnormal laboratory finding), symptom, or disease occurring after administration observed during the safety assessment period, regardless of causal relationship with the investigational product. However, if the AE worsens in grade or severity, it will be designated as a new AE.

The investigator (or subinvestigator) will assess AEs that occur in the subjects from the start of investigational product administration to the end-of-study assessment and record the results in the CRF.

(1) Symptoms and diseases

The investigator (or subinvestigator) will assess whether any AE has occurred in the subjects based on the interview and physical examination.

(2) Objective findings

The investigator (or subinvestigator) will identify any clinically significant abnormal finding* and handle it as an AE.

* “Clinically significant abnormal findings” will be identified according to the following criteria.

- Relationship to clinical signs or symptoms

- If these symptoms or signs are reported as AEs, the related abnormal laboratory findings and other test results will not be reported as separate AEs.
- Medical or surgical treatment of the abnormal laboratory test findings and other test results
- If the dosing regimen of the investigational product is changed (e.g., dose change, interruption, or discontinuation) due to abnormal results of laboratory or other tests.
- If the investigator (or subinvestigator) judges the abnormality as clinically significant for other reason(s).

(3) Assessments and criteria of AEs

1) Date of onset

The date of onset is defined as the date when symptoms are detected or the date when a laboratory test is performed for laboratory abnormalities. In this study, the onset time will also be recorded for all AEs occurring during hospitalization.

2) Severity

The severity of AEs will be classified as shown below.

1. Mild: The event does not interfere with the subject's activities of daily living.
2. Moderate: Causes some limitations in the subject's daily activities
3. Severe: The event interferes significantly with the subject's activities of daily living.

3) Seriousness

The seriousness of AEs will be classified as shown below.

1. Not serious: AEs not meeting the criteria listed in 2.
2. Serious: A serious AE (SAE) meets any of the following, from a) to g).
 - a) Death
 - b) A case which may lead to death

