7.1.2 Safety Assessments

7.1.2.1 Adverse Events

Adverse events will be coded according to the MedDRA version 23.1.

(1) Adverse Events (AEs)

An AE is any untoward medical occurrence or unintended sign (including an abnormal laboratory finding), symptoms and disease, occurred after administration and observed in the safety assessment period, regardless of causal relationship with the investigational product. However, if an existing AE worsens in grade or severity, it will be treated as a new AE.

(2) Serious Adverse Events (SAEs)

An AE is treated as a SAE if the seriousness was classified as “serious”.

(3) Adverse Drug Reaction

An AE is considered “adverse drug reaction” if the relationship to the investigational product was assessed to be “reasonable possibility”.

(4) Time to Adverse Events

Time to Adverse Events (days) = AE start date – date of administration in the period of AE occurrence + 1

(5) Duration of Adverse Events

Duration of Adverse Events (days) = AE stop date – AE start date + 1

(6) Period of Adverse Events occurrence

AEs will be assigned to the last administration of the investigational product before the occurrence.

Period I: AEs occurred on or after the time of administration in Period I but before the time of administration in Period II

Period II: AEs occurred on or after the time of administration in Period II but before the completion of end-of-study assessment.

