7.1.2.2 Laboratory Tests

(1) Clinically relevant values flag

Clinically relevant values flag will be attached to the values out of normal range. (L=Lower than normal range, H=Higher than normal range or A=Abnormal).

(2) Laboratory test values below the limit of quantification

Any BLQ data will be treated as LLOQ/2 in summary statistics.

7.1.2.3 12-Lead ECG

(1) Criteria for pre-defined limit

12-lead ECG:

- QTcF > 500 msec
- 500 >= QTcF > 480msec
- 480 >= QTcF > 450msec
- QTcF <= 450 msec
- Change from baseline in QTcF > 60 msec
- Change from baseline in QTcF > 30 msec

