7.2 Analysis Visit Definitions

(1) Non-PK related

Analysis visit window is not defined. By-visit summaries will be based on nominal visit or timepoint.

Study day is the relative day to the first treatment. Day -1 is the day before the first treatment, Day 1 is the day of the first treatment, and Day 2 is the next day.

Except for laboratory tests, Day 1 pre dose will be the baseline for Period I and Day 4 pre dose will be the baseline for Period II. For laboratory tests, Day -1 will be the baseline.

(2) PK related

Analysis time point and allowable range is defined below.

Analysis Time Point	Window
Predose	Within 60 min before dosing
0.083 h	Nominal time \pm 1 min
0.25, 0.5, 0.75, 1, 1.5, 2, 4, 6, 8, 10, 12 h	Nominal time \pm 5 min
24, 36, 48 h	Nominal time \pm 15 min

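### Does the SAP leave QTcF limit breaches unreported because it counts them only by time point and keeps unscheduled and withdrawal ECGs out of the tables?

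*SAP*

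**What the plan says.** SAP 7.1.2.3 defines four QTcF bands (above 500, above 480 to 500, above 450 to 480, and 450 msec or less) and two change limits, above 60 msec and "Change from baseline in QTcF > 30 msec". SAP 8.2.4 reports them in one way: "The percentage of subjects with values outside pre-defined limits will be summarized by treatment and time point". The same section summarizes QTcF and its change from baseline by treatment and time point, and requires all ECG data to be listed.

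SAP 9.3 gives the ECG time points: screening, Day -1, then pre-dose, 1, 24 and 48 h in each period, and end of study. It adds: "Unscheduled tests and tests on discontinuation will not be included in by-visit summaries but will be shown in listings". For baseline, SAP 7.2(1) states that "Day 1 pre dose will be the baseline for Period I and Day 4 pre dose will be the baseline for Period II".

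Protocol 9.1, footnote a, foresees ECGs at withdrawal: "At the time of withdrawal, perform the same tests as would be performed in the end-of-study assessment". Protocol 13.4.3(3) sets the ECG analysis: descriptive statistics at each time point and changes from baseline, separately for oral and nasogastric dosing.

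**The concern.** Safety is in the secondary objective and 12-lead ECG is a named safety assessment (SAP 2.1 and 2.1.1). A plan that defines QTcF limits might be expected to report how many subjects crossed each one on each route. This plan reports only percentages at each scheduled time. A subject who crosses a limit twice appears twice, and one who crosses it only on an unscheduled or withdrawal ECG does not appear in the limits table at all.

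The contrast with adverse events sharpens the impression. SAP 8.2.1 counts a subject once, at the worst severity, and SAP 7.1.2.1(6) gives a route rule: "AEs will be assigned to the last administration of the investigational product before the occurrence". QTcF has neither. Nor do the AE tables stand in for it, because Protocol 9.2.5.2(2) has the investigator identify "any clinically significant abnormal finding* and handle it as an AE". A breach not judged clinically significant never becomes an AE.

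If this were a real gap, a difference in QTcF breaches between routes could go untabulated.

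**Working it through.** The plan states no figure for this point, so the check compares what is required with what is delivered, and then asks what the planned output can and cannot show.

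**1. Required against delivered.**

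| Item | Protocol 13.4 and 13.4.3(3) | SAP 6.1, 8.2.4, 9.3 |
|---|---|---|
| ECG values by route and time point | Yes | Yes, with n, mean, SD, median, minimum, maximum |
| Change from baseline by route and time point | Yes | Yes, same statistics |
| QTcF limits by route and time point | Not requested | Added |
| Subjects with any post-dose breach | Not requested | Not promised |
| Listing of all ECGs | Not mentioned in this section | Yes, including unscheduled and withdrawal ECGs |

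Everything required is delivered, and more.

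**2. What the scheduled tables show.** Each route has three scheduled in-period post-dose ECGs: 1, 24 and 48 h (Protocol 9.2.5.1(3)). Let a, b and c be the numbers of subjects over one threshold at these times, and n the number dosed by that route. The number with any breach at these times lies between max(a, b, c) and min(n, a + b + c).

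- (0, 0, 0): exactly 0.
- (1, 0, 0): exactly 1.
- (1, 1, 1): 1 to 3 subjects; 1/36 = 2.8% to 3/36 = 8.3%.
- (2, 2, 2): 2 to 6 subjects; 2/36 = 5.6% to 6/36 = 16.7%.

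The counts are assumed, and the percentages take all 36 as dosed by that route. The range opens only when breaches occur at two or more times. The maximum QTcF and maximum rise, tabulated at each time on each route, also show whether anyone crossed a limit at a scheduled time and by how much.

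**3. Where this bound does not apply.** It holds for a single threshold: above 500 msec, and rises above 30 or above 60 msec. It does not describe a count of subjects by the band of their highest value. A subject at 460 msec at 1 h and 490 msec at 24 h gives (1, 0, 0) in the band above 450 to 480, so the maximum is 1, yet the highest-value count for that band is 0. In the lowest band a subject qualifies only if every value is 450 msec or less. Among subjects with all three ECGs, that count cannot exceed min(a, b, c). That band is also not a breach.

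**4. What the listings add.** A completer has 3 + 3 + 1 = 7 scheduled post-dose ECGs, so 36 completers give 36 x 7 = 252 listed records, plus any unscheduled ones. With a pre-dose baseline in each period, each listed in-period value can be compared with its own baseline. For a subject who leaves after the 1, 24 or 48 h ECG and has only the withdrawal ECG as an extra, the table holds 1 of 2, 2 of 3 or 3 of 4 post-dose ECGs on the last route. The listing holds them all.

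**5. Rises that stay at or below 450 msec.** A rise above 30 msec from below 450 - 30 = 420, or above 60 msec from below 450 - 60 = 390, can end within the lowest band. Such rises are still captured at every scheduled time by the two change limits.

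**6. Whether a pooled count would be cleaner.** It would need a route for the end-of-study ECG, taken 7 ± 2 days after the last dose. The earliest is 5 x 24 = 120 h. With the longest suspension half-life quoted in Protocol section 1 (11.8 h), that is 120/11.8 = 10.2 half-lives, so attributing it to one route is doubtful. Giving it to the second route balances scheduled post-dose ECGs at 18 x 3 + 18 x 4 = 126 per route only if all 36 complete, while Protocol 6.1 allows for 6 dropouts. As an assumed case, suppose all six leave the oral-first group after Period I. Oral then has 18 x 3 + 18 x 4 = 126 and nasogastric 18 x 3 + 12 x 4 = 102.

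**The case for a change.** The best case for the concern is that a plan which defines outlier limits should give the basic number they imply, subjects with any breach per route. That number cannot in general be rebuilt from time-point percentages, and withdrawal ECGs are foreseen, not hypothetical. The SAP already counts AEs by subject. The pre-dose ECG baseline in each period means that the reason given in SAP section 10 for dropping route summaries of laboratory tests does not apply here. An extra count would also be cheap: 6 rows x 2 routes = 12 figures from data already collected.

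The factual parts stand. No such table is planned, and a breach seen only on an unscheduled or withdrawal ECG, if not judged clinically significant, reaches the listings alone. What does not follow is that the plan is wrong. Keeping irregular and possibly triggered tests out of by-visit summaries is a sensible rule. It is stated openly, applies equally to vital signs and laboratory tests, and would stay in place even if the row were added. The AE analogy is weak, because AEs have no scheduled measurement times and are naturally counted by subject, whereas ECGs are. A clinically significant finding, scheduled or not, is to be handled as an AE and so enters the safety tables by that path.

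**Conclusion.** The concern does not hold. Followed as written, the plan meets Protocol 13.4.3(3), goes beyond it with the QTcF limits, and loses no data. The per-subject count is absent from the tables but can be made from the listings, and the scheduled tables already fix it for a single threshold unless breaches occur at two or more times.

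The sample size, the primary PK comparison and every stated rule are unaffected. The number of subjects for whom an extra row would differ from the planned table cannot be estimated from the documents.

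This rests on the listings being produced in full, as SAP 8.2.4 and 9.3 state, and on the study staying near 36 subjects, where a count from listings is practical. An any-time post-dose row would be an optional presentation choice.
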